7.2 CONCOMITANT DISEASES AND MEDICATION

Descriptive statistics are planned for concomitant therapy collected in eCRF. Medications will be coded by World Health Organization Drug Dictionary (WHO-DD) version Sep 2019.

Medication collected in eCRF “Concomitant therapy” will be classified as Prior only if start and stop prior to the date of first dose of study medication, if a medication starts before the date of first dose of study medication and stops on or after the date of first dose of study medication, then the medication will be classified as both Prior and Concomitant. Medications will be classified as Concomitant only if they have a start date on or after the date of first dose of study medication.

If medication start and/or stop dates are missing or partial, the dates will be compared as far as possible with the date of first dose of study medication. Medications will be assumed to be Concomitant only, unless there is clear evidence (through comparison of partial dates) to suggest that the medication started prior to the first dose of study medication. If there is clear evidence to suggest that the medication started prior to the first dose of study medication, the medication will be assumed to be both Prior and Concomitant, unless there is clear evidence to suggest that the medication stopped prior to the first dose of study medication. If there is clear evidence to suggest that the medication stopped prior to the first dose of study medication, the medication will be assumed to be Prior only.

Incomplete dates of medication/therapy will be imputed as detailed below:

Start Date: If start date is completely missing and end date is not prior to first dosing, then the medication will be classified as concomitant. If start date is completely missing and end date is prior to first dosing, then the medication will be classified as prior.

If (year is present and month and day are missing) or (year and day are present and month is missing) then set month and day to January 1. If year and month are present and day is missing then set day to first day of month.

End Date: If end date is completely missing then the medication will be classified as concomitant. If (year is present and month and day are missing) or (year and day are present and month is missing) then set month and day to December 31. If year and month are present and day is missing, then set day to last day of the month.

Note: if both start and end dates are missing, then the medication will be classified as concomitant only if there is no other evidence to indicate medication start before first study treatment, and classified as prior and concomitant if there is evidence to indicate medication start before first study treatment.

The following summary will be provided:

- A summary of prior therapy for study 1200-0318 (Analysis set: Treated Set)
- A summary of prior therapy compared between study 1200-0318 and 1200-0066 (Analysis set: Treated Set)
- A summary of concomitant therapy (Analysis set: Treated Set))

Proprietary confidential information © 2024 Boehringer Ingelheim International GmbH or one or more of its affiliated companies

7.3 TREATMENT INITIATION

A summary of number of subjects with at least one afatinib dose modification and number of afatinib modifications will be provided.

7.4 METHODS ADDRESSING BIAS

As described in [Section 7.1](#), channelling bias can occur due to preferential prescribing in relation to different risks for the events of interest. For example, if the sequential therapy would be prescribed more often compared with other treatments to high risky Chinese patients with EGFR mutation positive NSCLC (e.g., patients in this study are more severe than other Chinese EGFR mutation positive NSCLC patients or with more comorbidities at baseline). Thus, more incidences of outcome events were expected in the group with the sequential therapy (e.g., the incidence rates of AEs/ADRs will be affected). To assess the presence of the bias, we plan to use the data from study 1200-0066 to put the results into perspective to compare baseline demographic and clinical characteristics of the NSCLC patients. Through this, we can verify that safety or efficacy difference is due to patient baseline characteristics or the sequential therapy.

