9. RESEARCH METHODS

9.1 STUDY DESIGN

This is a NIS to be conducted at approximately 10 sites in China where real world data are from EGFR mutation positive NSCLC patients who will initiate afatinib as first-line treatment and receiving subsequent therapy. All the study sites will need to have afatinib used in regular clinical practice. Participating investigators will screen patients for eligibility, obtain informed consent, and enrol patients who meet the eligibility criteria. Investigators or trained site personnel will then complete the eCRF to capture information on demographic, medical history, and treatment information at the time of enrolment.

This study will only include patients who are newly diagnosed and who will receive afatinib as first-line treatment, regardless if they will receive 3rd generation or other treatment subsequently. Data will be collected for the patients who receiving afatinib first-line therapy and subsequent therapy. Data of patients' resistance mechanism after afatinib treatment will also be collected.

Day 0 is the date that the patient sign the informed consent . Day 1 is the first dose of afatinib. We collected the date of initial and metastatic diagnosis. Day 1 is the first dose of afatinib therapy (index date). The patients will be followed up by regular visits according to institution standards after start of afatinib until death, lost to follow-up, withdraw from the study, or end of the study for other reasons, whichever comes first and no later than Dec 2023. Please refer to [Section 4.1](#) for the visit plan and major information collected during each visit.

This study is descriptive only and there are no comparisons between groups. To assess the presence of this bias (discussed in [Section 9.9](#)), data from 1200.0066 study [where patients were diagnosed with locally advanced or metastatic NSCLC harbouring EGFR mutation(s)] may be used to verify if this study contains potential channelling bias.

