9.3.3 Covariates

As mentioned previously, the data from study 1200-0066 will be used to assess presence of potential channelling bias and to put the results into perspective. Therefore, the baseline characteristics of patients in 1200-0066 trial will be described. The covariates to be collected in the both studies (if applicable) are listed as following.

- Baseline demographic: age, gender, height, weight, body mass index, , smoking status (former, current, never)
- Clinical characteristics including medical history, surgery history, lab testing information (haematology, biochemistry and urine examinations), disease stage, tumour histological classification, EGFR mutation at start of afatinib therapy, ECOG PS score, brain metastases, afatinib starting dose
- Current/Concomitant medications

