9.9.2 Channelling bias

Channelling bias can occur due to preferential prescribing in relation to different risks for the events of interest. For example, if afatinib therapy would be prescribed more often compared with other treatments to high risky Chinese patients with EGFR mutation positive NSCLC (e.g., patients in this study are more severe than other Chinese EGFR mutation positive NSCLC patients or with more comorbidities at baseline). Thus, more incidences of outcome events were expected in the group with afatinib therapy (e.g., the incidence rates of AEs/ADRs will be affected). Furthermore , all patients who fulfil eligibility criteria and provide written informed consent will be enrolled. as patients with severe disease or other disabilities (eg those who are likely to have poorer outcomes) may be excluded from the study. This study is descriptive only and there are no comparisons between groups. To assess the presence of the bias, we plan to use the data from study 1200-0066 to put the results into perspective to compare baseline demographic and clinical characteristics of the NSCLC patients. Through this, we can verify that safety or efficacy difference is due to patient baseline characteristics or the sequential therapy.

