7.1 DEMOGRAPHIC AND OTHER BASELINE CHARACTERISTICS

Only descriptive statistics are planned for this section of the report. Demographic and baseline characteristic parameters collected and to be presented include:

- Age [years]
- Age class (<65, ≥ 65 years)
- Gender (Male, Female)
- Race (as defined in the eCRF)
- Height [cm]
- Weight [kg]
- Body mass index (BMI) [kg/m^2] (defined as weight [kg]/(height [cm]/100)²)
- Smoking status (Former, Current, Never)
- Baseline ECOG score
- EGFR mutation type
- Comorbidity history
- Surgery history
- Tumor histology classification
- Disease stage at the start of afatinib

Proprietary confidential information © 2024 Boehringer Ingelheim International GmbH or one or more of its affiliated companies

- Metastases at the start of afatinib
- Afatinib starting dose at baseline
- Medical history
- Prior therapy

In addition, to assess the presence of channeling bias, the data from study 1200-0066 will be used to assess potential channeling and to put the results into perspective. The baseline characteristics listed above (Except for Race) in this study and in study 1200-0066 will be presented separately. Patient characteristics will be compared between the two studies using absolute standardized differences (ASD), where an ASD of at least 10% will be considered a meaningful difference.

For continuous variable:

$$ASD = \frac{|(mean_1 - mean_2)|}{\sqrt{(s_1^2 + s_2^2)/2}}$$

- $mean_1$ is the arithmetic average of the analysed variable for study 1200-0318.
- $mean_2$ is the arithmetic average of the analysed variable for study 1200-0066.
- s_1 is the standard deviation of the analysed variable for study 1200-0318.
- s_2 is the standard deviation of the analysed variable for study 1200-0066.

For binary categorical variable:

$$ASD = \frac{|(p_1 - p_2)|}{\sqrt{(p_1(1 - p_1) + p_2(1 - p_2))/2}}$$

- p_1 is the rate of the analysed variable for study 1200-0318.
- p_2 is the rate of the analysed variable for study 1200-0066.

For categorical baseline variables with levels, Dalton (2008) proposed to use a multivariate Mahalanobis distance method to generalize the standardized difference metric to handle a multinomial sample [\[3\]](#):

$$T = (p_{12}, p_{13}, \dots, p_{1k})'$$

$$C = (p_{22}, p_{23}, \dots, p_{2k})'$$

$$p_{jk} = Pr(\text{category } k \mid \text{treatment group } j), j \in \{1, 2\}, \text{ and } k \in \{2, 3, \dots, k\}$$

$$ASD = \sqrt{(T - C)'S^{-1}(T - C)}$$

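### A baseline comparison with study 1200-0066 cannot show what caused a safety or efficacy difference, although SAP 7.4 and protocol 9.9.2 say it can

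*SAP*

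**What the plan says.** Both documents raise channelling bias and name a comparison with study 1200-0066 as the way to assess it. The therapy said to be channelled differs between them. Protocol 9.9.2 gives the example "if afatinib therapy would be prescribed more often compared with other treatments to high risky Chinese patients". SAP 7.4 gives "if the sequential therapy would be prescribed more often compared with other treatments to high risky Chinese patients".

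The stated method is "to compare baseline demographic and clinical characteristics of the NSCLC patients". Both sections then conclude: "Through this, we can verify that safety or efficacy difference is due to patient baseline characteristics or the sequential therapy".

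The supporting detail is in four places:

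- SAP 7.1: "The baseline characteristics listed above (Except for Race) in this study and in study 1200-0066 will be presented separately". ASDs follow, with 10% or more counted as meaningful.
- SAP 7.2: "A summary of prior therapy compared between study 1200-0318 and 1200-0066".
- Protocol 9.1, with the same statement in 9.9.2: "This study is descriptive only and there are no comparisons between groups".
- SAP 7.5, on confounding and effect modification, is marked not applicable.

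Protocol 9.11 goes further and counts the use of 1200-0066 among the efforts to minimise both channelling and attrition bias.

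**The concern.** The sentence gives the study an inferential property that its design lacks. Attributing an outcome difference needs outcomes in both groups and some way to separate case mix from treatment. A side-by-side baseline table supplies neither.

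Two misreadings could follow in the study report. Similar baselines could be taken as evidence that afatinib was not channelled to particular patients. Or a difference between this study's results and those of 1200-0066 could be put down to treatment because the baselines match, or to baseline factors because they do not. SAP 7.4 is the SAP's section on methods addressing bias, so the report's discussion of bias is likely to rest on it.

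**Working it through.** No stated figure is at issue. The check is to list every use of 1200-0066 and ask what it can support.

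**Step 1. What is taken from 1200-0066**

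| Place | Use |
|---|---|
| Protocol 9.1 | May be used to check for channelling; describes the patients by disease and EGFR status, not by treatment |
| Protocol 9.3.3 | Baseline covariates, on a list for both studies qualified as where applicable |
| Protocol 9.7 | Baseline characteristics with ASDs |
| Protocol 9.9.2, SAP 7.4 | Baseline comparison, followed by the verification claim |
| Protocol 9.11 | Cited as minimising channelling and attrition bias |
| SAP 7.1 | Baseline characteristics with ASD formulas |
| SAP 7.2 | Prior therapy |

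Every variable precedes treatment. The analyses of time on treatment (SAP 7.6), overall survival and response (7.7), resistance (7.8.1) and safety (7.10) use this study's Treated Set, which SAP 6.3 draws from this study's enrolled patients.

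**Step 2. What attribution would need**

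- An outcome difference between the studies: none is planned in the visible text.
- A method to separate case mix from treatment: none, since SAP 7.5 is not applicable.
- A treatment contrast: none is defined, because neither document says what the 1200-0066 patients received.

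The claim fails on the first two alone, whatever the third turns out to be.

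**Step 3. The claim in protocol 9.11**

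A baseline table can describe a difference in case mix but cannot reduce one. It holds no information on losses during follow-up, so it does not bear on attrition bias.

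**Step 4. What the lists suggest about the reference patients**

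The protocol 9.3.3 list for both studies includes "brain metastases, afatinib starting dose". The SAP 7.1 list, of which only race is excepted, includes afatinib starting dose and also stage and metastases at the start of afatinib. These items fit patients who took afatinib. No passage says that the 1200-0066 patients did, and the protocol list carries its where-applicable qualifier.

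**Step 5. What follows if they all took afatinib**

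This uses the binary ASD formula in SAP 7.1 with assumed population prevalences, ignoring sampling error:

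ASD = |p1 − p2| / √{[p1(1 − p1) + p2(1 − p2)] / 2}

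Assume that 50% of each afatinib cohort is high risk.

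- Planned comparison, afatinib with afatinib: |0.50 − 0.50| = 0, so ASD = 0.00. The same holds for any prevalence common to both cohorts.
- Afatinib with other treatments, 30% high risk: 0.20 / √[(0.25 + 0.21)/2] = 0.20 / 0.480 = 0.42.
- Same, 40% high risk: 0.10 / √[(0.25 + 0.24)/2] = 0.10 / 0.495 = 0.20.
- Same, 45% high risk: 0.05 / √[(0.25 + 0.2475)/2] = 0.05 / 0.499 = 0.10.

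Channelling that would reach or exceed the 10% threshold against other treatments would give an ASD of zero in the planned comparison if it affected both afatinib cohorts equally. The prevalences only illustrate the logic; the documents give none.

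**The case against.** The best defence is that the comparison has a legitimate use which the documents already state: to put the results into perspective. Protocol 9.9.2 worries that these patients may be more severely ill than other Chinese patients with EGFR-mutated disease, and that the sickest may be left out. An external baseline table can describe that. The protocol also says, in the same paragraph as the claim, that no groups are compared. All of this stands and is a reason to keep the table. It does not rescue the verification sentence, and SAP 7.4 does not repeat the caution.

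Four stronger readings are tempting, and the documents do not support them:

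- **That 1200-0066 is an afatinib cohort, so channelling cannot be assessed.** This is an inference from covariate lists that may simply be this study's own list reused. Channelling towards afatinib is also the protocol's example only. Under the SAP's wording, afatinib patients who did not receive the sequence could be a relevant contrast.
- **That sequential therapy has been dropped altogether.** It is not in the version 3.0 objectives, but protocol 9.2.1 still covers second-line treatment and SAP 7.7.1 plans a swimlane plot of survival by subsequent treatment.
- **That SAP 7.5 is itself a defect.** Not applicable is the expected entry for a descriptive single-arm study. It matters only because SAP 7.4 claims an attribution that would need such methods.
- **That no outcome comparison exists anywhere.** Protocol 9.7.2 and some SAP section numbers are absent from the public text and may have been redacted. The safe statement is that none is visible.

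**Conclusion.** The verification sentence in SAP 7.4 and protocol 9.9.2 is wrong as written and should be changed. The visible plan has no outcome comparison with 1200-0066 and no adjustment, so it cannot attribute a safety or efficacy difference to baseline characteristics or to therapy. This conclusion does not depend on what the 1200-0066 patients received. It assumes only that the missing sections hold no such comparison, which agrees with the protocol's statement that groups are not compared.

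A second conclusion is conditional. If all 1200-0066 patients took afatinib, the comparison cannot show preferential prescribing of afatinib over other treatments. The covariate lists point that way but do not establish it.

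The effect is confined to interpretation. No estimate of time on treatment, overall survival, response rate or safety changes.

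**What to change.** 1. Delete the verification sentence from SAP 7.4 and protocol 9.9.2.
2. In both places, describe the ASD comparison as case mix relative to 1200-0066 that puts the results into perspective. State that no outcome difference from 1200-0066 will be attributed to treatment or to baseline factors.
3. Remove from protocol 9.11 the claim that this comparison minimises channelling and attrition bias.
4. State what the 1200-0066 patients received. If all received afatinib, add that channelling to afatinib rather than other treatments cannot be assessed from these data.
5. Align the references to sequential therapy in SAP 7.4 with the protocol version 3.0 objective of first-line afatinib.

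The cost is a few sentences of text. No new data, analysis or programming is needed, and the ASD tables stay as planned. The sponsor gives up only a claim that the design cannot support.

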7.5 METHODS ADDRESSING CONFOUNDING / EFFECT MEASURE MODIFICATION

Not applicable.

7.6 PRIMARY ANALYSES

All patients treated with afatinib will be included in the analysis of the primary outcome, Time on Treatment (TOT) on afatinib.

The TOT with afatinib is defined as time from the start of afatinib to last dose date of afatinib or death date by any cause, which comes first.

Refer to Table 7.6: 1 for the rules for determining TOT with afatinib event or censoring date. The analysis of TOT with afatinib will be performed on Treated Set (TS). Those analyses will be conducted as one of the interim analyses mentioned in [section 7.11](#).

Table 7.6: 1 Rules for determining TOT event or censoring date

Rule #	Situation	Outcome	Date of event or censoring
1	Patients lost to follow up without providing end date of treatment during afatinib treatment period	censor	Date of last known date of contact during afatinib treatment period
2	Patients still receive ongoing first-line afatinib treatment at end of study period	censor	Date of last known date of contact during first line afatinib treatment period

Proprietary confidential information © 2024 Boehringer Ingelheim International GmbH or one or more of its affiliated companies

Rule #	Situation	Outcome	Date of event of censoring
3	Other situations	event	Date of last treatment during first line afatinib treatment period

The last known date of contact will derive as follows:

For subjects who withdrew from study or became lost to follow-up, the date last known of contact will be based on the last assessment date/visit date or the date of the last dose of study drug or end of study date, whichever occurs later.

If last known of contact date is later than cut-off date, use cut-off date as last known of contact date.

Kaplan-Meier estimates and two-sided 90% confidence intervals for the 25th, median, and 75th percentiles of the survival distribution will be calculated, the Brookmeyer-Crowley method^[4] based on log-log transformation will be used to construct the 90% CI, the standard error of the Kaplan-Meier quartile estimates will be estimated using Greenwood's formula. Kaplan-Meier curves will also be produced.

For the purpose of calculating TOT, incomplete first line afatinib treatment end dates will be imputed as below:

If month and year are present and day is missing:

- If year=year of first dosing and
 - If month = month of first dose then set day to day of first dose
 - If month > month of first dose then set day to first day of month
- If year > year of first dose then set day to first day of month

For all other cases, the missing dates will not be imputed and the subject will censored at last known of contact date and censored situation will be missing treatment end date.

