Name of finished medicinal product: Giotrif®				
Name of active ingredient: Afatinib				

withdraw before the end of study will be censored at the time of last known contact.
 
Secondary outcomes
 
Overall survival (OS) from the start of afatinib until the date of death, loss to follow up (including patient withdrawal) or end of study period
 
Objective response rate (ORR), [objective response is defined as best overall response of complete response (CR), partial response (PR)] according to RECIST 1.1 with afatinib first-line therapy
 
Adverse events (AEs), serious adverse events (SAEs), afatinib-related AEs (ADRs) as indicated by incidence, seriousness and intensity graded according to United States (US) national cancer institute's (NCI) common terminology criteria for AEs version 5.0 (CTCAE Version 5.0)
 
Further outcome
 
Resistance mechanisms (Type and proportion:T790M,etc) after afatinib first-line treatment.
				
Data sources:	
Data for this study will be obtained via the following sources:
 
- Patient medical information: The investigator or authorized medical staff will record clinical and treatment data from patients' medical records into an electronic case report form (eCRF) at baseline and at every visit up to end of the follow up period (refer to Section 9.4)			
Study size:	76 patients			
Study duration:	The duration of data collection for an individual patient will be a maximum of approximately 33 months, It is anticipated that all data collection for this study started from May 2020(first patient enrolled) and will continue until December 2023 (two years after the last patient was enrolled)			
Data analysis:	
Time on treatment (TOT) will be analysed using Kaplan-Meier method, and the median Time on Treatment (TOT) along with two-sided 90% confidence interval (CI) will be calculated. Overall survival (OS) will be analysed similarly.
 
Objective response rate (ORR) and acquired resistance mutation type, and AEs will be summarised descriptively by frequency and proportions.
			
Milestones:				
IRB/IEC Approval: May 2020				
First Patient In: May 2020				

Name of company: Boehringer Ingelheim		
Name of finished medicinal product: Giotrif®		
Name of active ingredient: Afatinib Last Patient In: Dec 2021 Interim Analysis: Dec 2022 Last Patient Out: Dec 2023 Database Locked: Mar 2024 Final NIS Report: Jun 2024		

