9.7.1 Main analysis

All patients treated with afatinib will be included in the analysis of the primary outcome, Time on Treatment (TOT) on afatinib. Time on Treatment (TOT) will be evaluated by Kaplan-Meier analysis. Median Time on Treatment (TOT) and two-side 90% CI, and the quartiles will be calculated from the Kaplan-Meier curve. Patients who are lost to follow up without providing the end date of treatment with afatinib will be censored at the time of last known contact.

Overall survival (OS) will be evaluated by Kaplan-Meier analysis. Median overall survival (OS) and two-side 90% CI, and the quartiles will be calculated from the Kaplan-Meier curve. Patients who are lost to follow up (including patient withdrawal) without providing the end date of treatment will be censored at the time of last known contact. Patients who reach the end of study period without providing the end date of treatment will be censored at the end of study.

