5. OUTCOMES

5.1 PRIMARY OUTCOMES

- Time on treatment of afatinib (ToT) as first-line therapy in advanced non-small cell lung cancer patients with EGFR mutation. Time on treatment is defined from the start of afatinib treatment until the end of the afatinib treatment or death date by any cause. Patients that are lost to follow up or withdraw before the end of study will be censored at the time of last known contact.

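### SAP Table 7.6:1 has no censoring row for study withdrawal, so a patient who withdraws on afatinib with a last-dose date counts as a time-on-treatment event, against SAP 5.1 and the protocol

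*SAP*

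**What the plan says.** **Outcome definition.** SAP 5.1 states: "Patients that are lost to follow up or withdraw before the end of study will be censored at the time of last known contact". The protocol abstract ("withdraw before the end of study will be censored at the time of last known contact"), section 8 and section 9.3.2.1 give the same rule.

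**Operative rule.** SAP Table 7.6:1 has three rows:
- Rule 1 censors "Patients lost to follow up without providing end date of treatment during afatinib treatment period".
- Rule 2 censors patients whose first-line afatinib is ongoing at the end of the study period.
- Rule 3 is the catch-all. Its outcome is an event, dated "Date of last treatment during first line afatinib treatment period".

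**Text around the table.** The derivation of last contact begins "For subjects who withdrew from study or became lost to follow-up, the date last known of contact will be based on" and includes the last dose of study drug among its inputs. An end date given as month and year is imputed. For end dates that cannot be imputed, "the subject will censored at last known of contact date and censored situation will be missing treatment end date".

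**Protocol 9.7.1.** The TOT sentence reads "Patients who are lost to follow up without providing the end date of treatment with afatinib will be censored" and does not mention withdrawal. The overall survival sentence does: "Patients who are lost to follow up (including patient withdrawal) without providing the end date of treatment will be censored".

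SAP section 4 declares no change to the planned analysis.

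**The concern.** Leaving the study is not the same as stopping the drug. A patient who withdraws consent while still taking afatinib has an unknown treatment end, and the outcome definition accordingly censors that patient. The table has no row that does so, and its catch-all counts the patient as having ended treatment.

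TOT is the sole primary outcome, and protocol 9.5 allows for 30% dropout among 76 patients. One programmer working from SAP 5.1 and another working from the table would code the same patient differently. The resulting bias has one direction. Replacing a censored time by an event at the same or an earlier time can leave the Kaplan-Meier curve unchanged or lower it, but cannot raise it.

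**Working it through.** **Step 1: which withdrawals reach Rule 3?** Take a patient who withdraws while taking afatinib.

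| Afatinib end date in the database | SAP 5.1 | SAP 7.6 |
|---|---|---|
| Missing, not imputable | censor | censor (missing-date sentence) |
| Month and year only | censor | date imputed, then Rule 3: event |
| Complete last-dose date | censor | Rule 3: event |

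Reading loss to follow-up in Rule 1 as including withdrawal, as the overall survival wording does, does not help: Rule 1 still requires that no end date was provided. Rule 2 does not help either. Protocol 9.7.1 treats the end of the study period separately from withdrawal, so it means the end of the study, not the patient's own exit.

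**Step 2: inputs.**
- From protocol 9.5: N = 76, exponential TOT with median 12 months, 30% dropout. Hazard L = ln2/12 = 0.0578 per month.
- From protocol section 6: entry May 2020 to December 2021 (19 months), last patient out December 2023, so follow-up is 24 to 43 months.
- Assumed: uniform entry and independent exponential dropout with hazard d. A share f of on-treatment dropouts are withdrawals that reach Rule 3. The documents give neither f nor the time scale of the 30%, so two time scales are shown.

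**Step 3: the plan's own figures.** Protocol 9.5 expects 35 events. This does not reproduce: 76 × 0.7 × (1 − 0.25) = 39.9 at 24 months of follow-up, and the fast scenario below gives about 48. That is a separate matter, and nothing here rests on it. The precision statement in protocol 9.9.3 (80% chance of a 90% CI no wider than 11 months) is met: the chance is about 0.92 in the fast scenario with all dropouts censored.

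**Step 4: median under Rule 3.** Coding a share f of dropouts as events changes the apparent hazard to L + f·d, so the median tends to ln2/(L + f·d).

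- *Slow*: 30% dropout by month 43, d = −ln(0.7)/43 = 0.0083. Expected on-treatment dropouts: 8.4 of 76.
- *Fast*: 30% of all patients drop out while on treatment, d = 0.0273. Expected: 0.30 × 76 = 22.8.

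| f | Slow: miscoded patients, median | Fast: miscoded patients, median |
|---|---|---|
| 0 | 0, 12.0 months | 0, 12.0 months |
| 0.25 | about 2, 11.58 | about 6, 10.73 |
| 0.50 | about 4, 11.20 | about 11, 9.71 |
| 1 | about 8, 10.49 | about 23, 8.15 |

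For example, slow with f = 0.5: 0.6931/(0.0578 + 0.5 × 0.0083) = 11.2.

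Capping follow-up at the 33 months in protocol 9.2.2 (range 24 to 33) changes the fast column little: 10.69, 9.64 and 8.05.

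**Step 5: simulation check, N = 76.** Simulated medians for f = 0.25, 0.5 and 1 were 11.6, 11.2 and 10.3 months (slow) and 10.7, 9.7 and 8.0 months (fast). With exactly 1, 2 or 4 miscoded withdrawals, the mean shift was −0.21, −0.40 and −0.81 month (slow) and −0.25, −0.48 and −0.98 month (fast).

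The interval also narrows. In the fast scenario the 80th percentile of the 90% CI width falls from 9.2 months to 7.8, 6.9 and 5.3 for f = 0.25, 0.5 and 1. The biased estimate would look more precise.

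**The case against.** The best defence is that the ordinary case is already handled. A patient who leaves while still taking afatinib has no treatment end to report. If the field is empty, SAP 7.6 censors at last contact, and the last-contact derivation names withdrawn subjects. Intent to censor is plain, and harm needs a site to enter a last-dose date as an end date merely because the patient left. The eCRF is not available, so how often that happens cannot be known.

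This stands as a limit on size, but it does not close the gap. The same derivation lists the last dose as an input for withdrawn subjects, so the SAP itself expects such dates to exist.

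Secondly, a true end date followed by withdrawal is a genuine event. For that patient Rule 3 is right, and SAP 5.1 read literally would wrongly censor. This stands in full: both texts need correction, and copying SAP 5.1 into the table would create the opposite error.

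Thirdly, the larger figures are extreme. The 8.2-month value needs all 30% dropout to occur on afatinib and every such patient to withdraw with a usable date. It is a ceiling. A patient miscoded at a time beyond the median does not move it. The study is descriptive, and its planning accepts a CI width of up to 11 months. All this is fair, but it does not justify leaving two incompatible rules for the primary outcome.

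**Conclusion.** The concern holds. For a patient who withdraws on afatinib with a recorded or imputable last-dose date, Table 7.6:1 gives an event, while SAP 5.1 and the protocol's outcome definition give censoring. Confidence in the contradiction is high; the size of the bias is conditional.

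It is zero if no such patient has a usable date. Otherwise it is about 0.2 month of median TOT per miscoded patient on average, always downward. The illustrative range from a true median of 12.0 months is 11.6 to 10.5 months under slow dropout and 10.7 to 8.2 months under fast dropout, the last being a ceiling. These figures rest on exponential TOT, independent exponential dropout, uniform entry, and an assumed share of dropouts reaching Rule 3. The point should be fixed, but it does not undermine the study.

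**What to change.** - **Rule 1:** extend it to patients lost to follow-up or withdrawn from the study without a documented afatinib discontinuation. Keep its censoring date, the last known contact during the afatinib treatment period.
- **Rule 3:** replace the catch-all by documented afatinib discontinuation or death on afatinib, regardless of later loss or withdrawal.
- **Definition:** state that a last-dose date recorded only because the patient left the study is not a documented discontinuation.
- **Alignment:** bring SAP 5.1 and protocol sections 8, 9.3.2.1 and 9.7.1, with the abstract, into line with the table, so that a true treatment end before withdrawal stays an event.

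The cost is a few lines in the SAP and a matching protocol clarification before database lock. Protocol 9.3 already collects the afatinib end date and the reason for discontinuation, so no new variable should be needed. The eCRF should be checked to confirm that these fields separate a study exit from a true discontinuation.
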